Protocol: In-person randomized control trial of the incidence of postoperative hypoesthesia among bilateral sagittal split osteotomy patients treated with ultrasonic vs. reciprocating saw instrumentation.

NCT05205616

May 30th, 2025

Table of Contents

RESEARCH STRATEGY OVERVIEW.....	2
STUDY PROCEDURES.....	3
TREATMENT:.....	3
DATA COLLECTION:.....	3
STATISTICS.....	4
OUTCOME OPERATIONALIZATION:.....	4
PRIMARY ANALYSIS:.....	4
SECONDARY ANALYSES:.....	4
QUALITY CONTROL / INTERIM ANALYSIS.....	5
HUMAN SUBJECTS.....	6

Research Strategy Overview

The aim of this prospective study is to analyze the postoperative paresthesias experienced in patients who undergo bilateral sagittal split osteotomies (BSSO) using an ultrasonic saw, versus a reciprocating saw. A matched-pair (with-in person) RCT design will be used, wherein each mandibular side (right versus left) in each patient will be randomized to be treated with either reciprocating saw (RemB) or Sonopet ultrasonic device (Sonopet IQ Hp). Patients included in the study are ages 15-45 scheduled to undergo BSSO surgery at the University of California, San Francisco. The orthognathic surgeries will be performed at UCSF Parnassus Moffitt-Long Hospital and UCSF Medical Center at Mission Bay, Benioff Children's Hospital. Follow-up appointments will be conducted at [name], Oral and Maxillofacial Surgery (OMFS) Faculty Practice Clinic.

One side of the patient's mandible will be instrumented with either the Stryker Sonopet ultrasonic saw or traditional reciprocating saw, while the other side will receive the remaining intervention (determined via randomization on the day of surgery). Patient paresthesias will then be analyzed on each side for 3 months postoperatively (at postoperative days: 1, 7, 14, 28, and 84). Sensory examinations will be carried out by blinded examiners using von Frey hairs and two-point discrimination testing. Patients will also subjectively rate their sensation on each side. The results will then be analyzed to determine if patient paresthesias, including the severity and duration, differed depending on which instrument was used, the ultrasonic or reciprocating saw.

Study procedures

Treatment:

On the day of surgery, a randomization process (using randomization blocks of 8, using sealedenvelope.com with a predetermined seed) will determine which mandibular side receives which intervention (Sonopet ultrasonic saw or reciprocating saw), as well as which side is operated on by [name], DDS, MD, with the remaining side being operated on by the senior resident involved with the case. Given the supervision of the attending surgeon, the senior resident has the appropriate skills to perform the equivalent procedure on the contralateral side. Given that the two osteotomy instruments are physically different, the provider delivering the treatment cannot be blinded. It will be documented in the operative report if the patient received any other interventions, such as LeFort I osteotomy or genioplasty, and if any direct manipulation of the inferior alveolar nerve occurred (for instance if the nerve was gently freed from the proximal mandibular segment, if the nerve was not directly visualized, etc.).

Data Collection:

Patient sensation in the V3 distribution will be analyzed on each side at one week preoperatively (baseline) and at five different postoperative timepoints: 1 day, 1 week, 2 weeks, 4 weeks, and 3 months. Patients are already and consistently under OMFS care at these timepoints (whether as an inpatient or at a clinic visit) thereby collecting this data will be at minimal inconvenience to the patient. Sensation will be evaluated with patients completing a Medical Research Council Scale questionnaire, along with residents testing sensation with von Frey hairs (at a region 1 cm below corresponding lower lip) and two-point discrimination tests with calipers (on corresponding lower lip).

The patient, as well as the resident evaluating the patient, will be blinded to which side received which intervention. Patient's medical records will not indicate which side was operated on with which osteotomy instrument, and the evaluating resident will be a different provider than the senior resident who delivered the treatment. To assess efficacy of observer blinding, the observing resident will guess at the time of sensory measurement which side of the patient was operated on using the ultrasonic saw. Also to verify measurement accuracy, a second observer ([name]) will reexamine the patient and verify the von Frey hair and two point discrimination findings that the resident collected at each visit.

Patient's age, gender, race/ethnicity, and intraoperative complications relating to osteotomy will also be recorded. Also, medication history (steroids, analgesics, psychiatric/neuroepileptic, etc...) will be recorded at each visit.

Statistics

Outcome operationalization:

For more practical clinical aim as a lower lip two point discrimination test >15mm, or patient's inability to sense third hair or thicker in the von Frey hair series.

Primary analysis:

Effect measure (Odds Ratio) of the intervention on neurosensory deficit at 3 months will be calculated in both an Intention to Treat (ITT) and Per Protocol (PP) analysis using conditional logistic regression models (an extension of McNemar's test). If the treatment and intervention arms are perfectly balanced and matched, age and gender will not be used as covariates.

However, effect measure modification (interaction) of these and other covariates (e.g. gender, age, specific medications) will be explored. Likely, very few patients will undergo unexpected intraoperative manipulation of the inferior alveolar nerve. These patients will be omitted from analysis, unless they represent >10% of the sample size, in which case, we will include the patients and adjust for them as a covariate in the conditional logistic regression.

Secondary analyses:

A subgroup time-to-recovery analysis will also be performed among those patients exhibiting neurosensory deficit in post-operative day 1. This analysis will be a survival analysis with follow-up period from day 1 to 3 months, with "failure event" being recovery of neurosensory deficit. If too few recoveries occur prior to 3 month visit, we will again use conditional logistic regression test instead. [Update: This analyses was not ultimately done due to small sample size at completion of study.]

Quality Control / Interim Analysis

For the first six months, all investigators and an on-field data collecting resident will meet monthly to discuss and assess challenges, progress, harms, and benefit. Any initial reports of deviation/adverse event/breaks in confidentiality will be reviewed immediately by the principal investigator and out-report in accordance with the UCSF post-approval reporting requirements. Thereafter, the research team will reconvene at a minimum of every three months. An unblinded interim analysis of efficacy and effect measure will be performed by the analytic investigator at 1 year (or at 25 patients, whichever is sooner) to assess for termination of trial due to unexpectedly strong benefit or harm.

Human Subjects

Patients will be identified from the UCSF Moffitt-Long and Mission Bay Benioff Children's hospital operating room schedules for [name], and those scheduled for BSSO surgery who meet the inclusion criteria will be approached for enrollment in the study. All patients scheduled for BSSO surgery with [name] will be approached for enrollment in the study. Exclusion criteria will be an age of over 45, and any preexisting mandibular sensory derangements. This study will aim to include 50 patient participants.

At each patient's presurgical clinic appointment, which occurs one week before their scheduled surgery date, they will be approached for enrollment by a resident. The resident will explain the study and emphasize that whether they decide to enroll or not will not affect their scheduled surgery date. It will be explained that on the day of surgery, randomization will decide which mandibular side will be instrumented with the Sonopet ultrasonic saw, with the remaining side receiving treatment with the traditional reciprocating saw. Both of these methods are an accepted and standard level of care for BSSO patients, commonly used in academic institutions across the country. We will then analyze their V3 paresthesias on each side at various timepoints postoperatively. [name] will see the patient next and will further answer any questions they have about the study. If the patient, or their legal guardian if they are under the age of 18, agree to be involved in the study they will then sign a paper consent form explicitly documenting this. Less than one hour- roughly 10 additional minutes will be added to each follow up appointment (5 in total) time to thoroughly assess their sensory function on each mandibular side.

Data will be stored immediately on collection using the secure and HIPAA-compliant online web application, REDCap. [name] will serve as data manager, programmer, analyst, and quality control coordinator. All patient records will be accessed from UCSF campus computers, therefore no PHI will be saved on personal computers or stored for later use. Any identifiable data collected for recruitment purposes (i.e. during patient approach and while gathering informed consent) will be discarded via shredder machine the same day should the patient not be interested in participating in the study. Only necessary information for the study will be kept regarding patients who do choose to participate in the study.

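### The promised ITT odds ratio omits patients on an undefined event that follows randomisation, and no unadjusted analysis of all randomised pairs is specified

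*Combined protocol and SAP*

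**What the plan says.** Under Statistics, Primary analysis, the 3-month odds ratio is to be estimated by conditional logistic regression "in both an Intention to Treat (ITT) and Per Protocol (PP) analysis". Neither set is defined anywhere. The next paragraph says "Likely, very few patients will undergo unexpected intraoperative manipulation of the inferior alveolar nerve", and continues: "These patients will be omitted from analysis, unless they represent >10% of the sample size". Above that threshold the plan will keep them and "adjust for them as a covariate in the conditional logistic regression". It does not say which of the two analyses the rule governs, or whether the covariate is coded per patient or per side.

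On timing, the Research Strategy Overview has the side allocation "determined via randomization on the day of surgery", so manipulation during the operation comes after it. On recording, Study procedures, Treatment, says the operative report will note "if any direct manipulation of the inferior alveolar nerve occurred". Its open-ended examples run from a nerve gently freed to a nerve not seen at all, with no line between expected and unexpected. The same section says "the provider delivering the treatment cannot be blinded".

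Human Subjects sets a target of 50 patients. The update under Secondary analyses reads "This analyses was not ultimately done due to small sample size at completion of study", which indicates that the study is finished and smaller than hoped.

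**The concern.** ITT keeps every randomised unit in the arm it was assigned to. Here a pair leaves the analysis because of something that happened in surgery, after assignment, and that the saw may have caused. If one saw leads to more nerve manipulation, and manipulation leads to numbness, the omission removes part of the effect the trial is meant to measure. Pairing gives no protection, because one side's event removes the whole pair.

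The trigger is also open to judgement. The plan does not say who decides that manipulation was unexpected, or that this is settled before unblinding. The operators know the instrument. The analytic investigator runs an unblinded interim analysis, and one person is both data manager and analyst. That the label is given with knowledge of the saw is an inference: the report's author is not named, and Data Collection says medical records will not show which instrument was used on which side.

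Only discordant pairs inform the paired odds ratio, and few may be available, so a handful of omitted patients can matter.

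**Working it through.** **Threshold.** 5/50 = 10% is not above 10%, so up to 5 pairs are dropped and 45 remain. With 6 flagged patients all are kept and the model changes. At 25 patients the limit is 2. The target of 50 comes with no error rate, power, deficit rate or effect size, so there is no planned figure to reproduce.

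**Inputs.** Only n = 50 and the 10% rule come from the plan. All rates below are assumptions, and sides are taken as independent. m is the manipulation probability per side (R reciprocating, U ultrasonic), d1 the deficit risk with manipulation (60%, or 30% in brackets) and d0 the risk without.

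**Formulas.** Deficit risk per saw: p = m·d1 + (1−m)·d0. All-pairs OR (ultrasonic vs reciprocating) = pU(1−pR) / [pR(1−pU)]. After omission the same expression uses d0 only. Flagged patients: X ~ Binomial(50, q), with q = 1 − (1−mR)(1−mU). The omission branch is X ≤ 5.

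**Scenario 1 in full** (mR 7%, mU 2%, d0 8%, d1 60%):
- pR = 0.07×0.60 + 0.93×0.08 = 0.1164; pU = 0.02×0.60 + 0.98×0.08 = 0.0904.
- All-pairs OR = (0.0904×0.8836)/(0.1164×0.9096) = 0.75. After omission both risks are 0.08, so OR = 1.00.
- q = 0.0886, P(X ≤ 5) = 0.72, E[X | X ≤ 5] = 3.44.
- Expected discordant pairs in the branch: 3.92 with deficit on the ultrasonic side only and 4.93 on the reciprocating side only. OR = 3.92/4.93 = 0.80.
- Discordant pairs fall from 8.86 to 6.85, a loss of 23%.
- SE of log OR = √(1/3.92 + 1/4.93) = 0.68. Shift = ln(1.00/0.795)/0.676 = 0.34 SE.

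| | Manipulation R vs U | d0 R, U | OR, all pairs | OR, omission branch | OR after omission | Discordant pairs lost | Shift in SE |
|---|---|---|---|---|---|---|---|
| 1 | 7% vs 2% | 8%, 8% | 0.75 (0.87) | 0.80 (0.90) | 1.00 | 23% (14%) | 0.34 (0.15) |
| 2 | 2% vs 1% | 8%, 8% | 0.94 (0.97) | 0.94 (0.97) | 1.00 | 11% (6%) | 0.09 (0.04) |
| 3 | 2% vs 7% | 8%, 6% | 1.09 (0.90) | 1.02 (0.87) | 0.73 | 25% (16%) | 0.46 (0.22) |

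The branch applies with probability 0.72, 0.996 and 0.72, with 3.4, 1.5 and 3.4 patients omitted on average. Scenario 2 is closest to the plan's own expectation. The 1.00 in scenarios 1 and 2 follows from assuming that the saw acts only through manipulation. In scenario 3 the direction changes only if d1 exceeds about 45% (all trials) or 57% (omission branch). At n = 25 and d1 = 60% the branch ORs are 0.84, 0.94 and 0.95, with 18%, 10% and 20% of discordant pairs lost.

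**Labelling with knowledge of the saw.** Take true manipulation of 5% with both saws, d0 = 8% and no direct effect. Let s be the chance that a manipulated side is called unexpected. Risk among uncalled sides = [m(1−s)d1 + (1−m)d0] / [m(1−s) + 1−m]. With s = 80% for reciprocating and 40% for ultrasonic, the risks at d1 = 60% are 0.0854 and 0.0959, so a true OR of 1.00 becomes 1.14 (1.06). With the calls reversed it becomes 0.88 (0.94).

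**Above 10%.** A patient-level flag has the same value on both sides, so it cancels from the conditional likelihood. In a worked data set the log-likelihood was −8.9974 at flag coefficients of 0, 3 and −5. The adjustment then does nothing. A side-level flag does not cancel. With manipulation 10% vs 4% and d0 = 8%, the OR is 0.74 (0.86) unadjusted and 1.00 adjusted, because the flag absorbs the saw's effect through manipulation.

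**One pair at the margin.** Exact McNemar gives 6:0 p = 2/2⁶ = 0.031 and 5:0 p = 2/2⁵ = 0.063; 8:1 p = 20/2⁹ = 0.039 and 7:1 p = 18/2⁸ = 0.070. The 5% level is assumed, since the plan names none.

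**The case against.** The best defence has four parts.

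- **The rule may be meant for PP only.** The plan promises both sets, and the omission sentence names neither. This is possible, but no text supports it, and the paragraph speaks simply of the analysis.
- **The branch above 10% may restore ITT.** The text speaks of patients, and a patient-level flag cancels, so the result would equal the unadjusted all-pairs OR. That is right for that coding. The coding is not stated, however, and the plan describes an adjusted model; an ITT result would arise there only by accident. The branch at or below 10%, which the plan expects, is unaffected.
- **The effect is small.** Every rate is assumed. Scenarios 1 and 3 flag 8.9% of patients, which sits poorly with very few. In simulation at n = 50, omission changed the 5% significance verdict in only about 1% to 2.5% of trials. The McNemar pairs above are chosen at the boundary. If nobody was flagged, the rule had no effect. If manipulation is equally likely with both saws and neither has a direct effect, the OR stays at 1.00; if a direct effect exists, omission changes what is estimated rather than biasing it. All of this stands and limits the size.
- **The remedy is itself post hoc, and covers only pairs with 3-month results.** Both are true. Disclosure and side-by-side reporting answer the first. The second is a separate matter of missing outcomes, which this change does not solve.

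The unblinding argument is the weakest part of the concern, because it rests on inference. The defect does not depend on it.

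**Conclusion.** The concern holds, and the plan should be corrected. Followed as written, the rule removes up to 5 of 50 randomised pairs for an undefined event after randomisation that the saw may cause, and the result would still be labelled ITT. That conclusion rests on the text alone. The numerical effect rests on assumed rates: from 0.94 to 1.00 where manipulation is rare, and from 0.80 to 1.00 or from 1.02 to 0.73 (omission branch, d1 = 60%) where it is commoner and differs by saw. The bias is less than half a standard error in every scenario examined and can go in either direction. The number of flagged patients and the final sample size are not in the documents, so the actual effect is unknown.

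**What to change.** Define the ITT result as the conditional logistic regression on all randomised pairs with a 3-month outcome, each side analysed as randomised, with no omission or adjustment for nerve manipulation. Remove the 10% switch. State which recorded events were counted as unexpected manipulation and who decided, and give their number, by instrument where the side is known. Report how many randomised patients lack a 3-month result. Keep the omission analysis and PP as sensitivity analyses only.

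Because the study appears complete, disclose this as a change made after data collection and print the analysis as planned beside it.

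The cost is one re-run on existing data plus the disclosure; no new data are needed. The drawbacks are a post hoc change to the primary analysis and possibly slightly more noise from the retained pairs.

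### A data-collecting resident attends monthly harm and benefit meetings, and nothing keeps side- or instrument-specific information out of them: an avoidable risk to assessor blinding

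*Combined protocol and SAP*

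**What the plan says.** The Data Collection section states the blinding rule without exception: "The patient, as well as the resident evaluating the patient, will be blinded to which side received which intervention". It assigns the outcome measurements to "residents testing sensation with von Frey hairs" and using two-point calipers. It supports the blinding in two ways: medical records do not show which instrument was used on which side, and the evaluator is a different resident from the one who operated. The evaluator also guesses the ultrasonic side at the time of measurement, and a second observer re-examines the patient at each visit.

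The Treatment section says that "the provider delivering the treatment cannot be blinded". The operators are the attending surgeon and a senior resident, one on each side.

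The Quality Control / Interim Analysis section says that, for the first six months, "all investigators and an on-field data collecting resident will meet monthly to discuss and assess challenges, progress, harms, and benefit". Then: "Thereafter, the research team will reconvene at a minimum of every three months". It adds: "An unblinded interim analysis of efficacy and effect measure will be performed by the analytic investigator at 1 year", or at 25 patients if that comes sooner.

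Nothing limits these meetings to pooled or masked information, sets up a closed session, or bars talk of allocation in front of an assessor.

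**The concern.** The protections in the Data Collection section cover the record and the choice of evaluator. They do not cover what is said aloud, and the protocol sets up a standing meeting where a data collector and the operators review harms and benefit together.

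The design makes a small leak costly. Each patient receives one saw per side, so learning the instrument on one side reveals the other. Attributing a harm or a benefit to a saw means linking it to a side, and with few patients early on, such talk can easily turn to individual cases. Those patients may still await the 3-month examination that decides the primary outcome. That outcome is a yes/no call from examiner-run tests (two-point discrimination above 15 mm, or a von Frey threshold), which leaves room for borderline readings. If an assessor who knew the allocation leaned one way, the paired odds ratio would be biased.

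**Working it through.** **Step 1: compare the rules.** The plan contains no figure to reproduce here, so the main check is on the text.

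- Must the assessor be blinded? Yes (Data Collection).
- Does someone who knows the allocation attend? All investigators attend, and whoever operates cannot be blinded (Treatment). Which investigators operate cannot be read from the public text, because names are removed.
- Does an assessor attend? A data-collecting resident does. Sensory data are collected by residents who must be blinded, so this is the natural reading, but it is not stated.
- Is information restricted at the meeting? No rule is stated.
- Do the other safeguards reach the meeting? No. The record rule and the separation of operator from evaluator do not govern discussion. The guess can signal that blinding failed but cannot prevent it.

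**Step 2: how many patients could be exposed.** The documents give the target (50), the follow-up (84 days) and the six-month monthly period. They give no accrual rate. Assume 25 patients per year; this borrows the two interim triggers as a convenient figure, and the plan does not state it as a rate.

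- Per month: 25/12 = 2.08
- In follow-up at a given meeting, at steady state: 2.08 × 84/30.4 = 5.8
- Entering in six months: 2.08 × 6 = 12.5, and 12.5/50 = 25% of the sample

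**Step 3: what a leak could do.** Assume no true effect, 50 complete pairs, a two-sided 5% McNemar test without continuity correction, and 20% discordant pairs (10% each way). The documents give neither an alpha nor a discordance rate. Let *f* be the fraction of patients leaked and *s* the rise, among them, in the probability of a deficit recorded on the reciprocating side only. The odds ratio (reciprocating versus ultrasonic) is

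OR = (0.10 + *f* × *s*) / 0.10.

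For *f* = 0.25 and *s* = 0.10: (0.10 + 0.025)/0.10 = 1.25. Type I error is the probability that (b − c)²/(b + c) exceeds 3.84, summed exactly over the multinomial for 50 pairs, where b and c are the two discordant counts.

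| Patients leaked | OR at *s* = 10 / 20 / 30 points | Type I error |
|---|---|---|
| None | 1.00 | 4.3% |
| About 3 (*f* = 0.06) | 1.06 / 1.12 / 1.18 | 4.4% / 4.6% / 5.0% |
| About 6 (*f* = 0.125) | 1.13 / 1.25 / 1.38 | 4.7% / 5.7% / 7.4% |
| About 12 (*f* = 0.25) | 1.25 / 1.50 / 1.75 | 5.7% / 9.7% / 16.1% |

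With the exact McNemar test, the last row runs from a baseline of 2.2% to 3.3%, 6.2% and 11.1%, so the direction does not depend on the test.

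**Step 4: range for the assumed discordance.** For *f* = 0.25, the same formula with 0.05 or 0.15 in place of 0.10 gives:

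- 10% discordance: OR 1.50 / 2.00 / 2.50; type I error 7.2% / 13.2% / 22.1% (baseline 4.7%)
- 30% discordance: OR 1.17 / 1.33 / 1.50; type I error 6.0% / 9.2% / 14.1% (baseline 4.7%)

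With about 3 patients leaked, type I error does not exceed 6.1% at any of the three discordance rates.

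**The case against.** A reader might infer that the two sections contradict each other, or that the protocol in effect unblinds its assessor. The text does not support that. The blinding rule has no exception, and the meeting rule sets attendance and agenda without authorising disclosure of allocation. Harms and benefit can be reviewed as pooled deficit rates or visit burden, which reveals no patient's side. What stands against the plan is narrower: it puts a data collector in that meeting and states no safeguard for it.

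Two links are inferences. The resident at the meeting is not said to be an evaluator of patients still in follow-up; several residents test patients, and residents also enrol them. Nor can the public text show which investigators know the allocation, beyond those who operate and the analyst at the interim.

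A reader might also infer that interim results would reach the assessor through the monthly meetings. At 25 patients per year the interim analysis falls at month 12, six months after those meetings end. Attendance at the later meetings is given only as the research team, so the resident's presence there is not established.

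The largest figures assume that every patient entering in six months is leaked and that all shifts run one way. In that subset the favourable discordant share rises from 10% to 20%, 30% or 40%, a within-subset odds ratio of 2, 3 or 4. A leak confined to a few recently discussed cases does much less.

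The second observer's re-measurement may catch distorted readings. It is only a partial answer, because that observer is not stated to be blinded.

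Finally, a note under Secondary analyses refers to completion of the study. If conduct has ended, a new meeting rule protects no data already collected.

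**Conclusion.** The concern holds as an avoidable risk to assessor blinding. It is not shown that any assessor was unblinded or that any result is biased. It depends on the meeting resident being one of the sensory assessors, and on case-level talk by side or instrument taking place; the plan neither states nor rules out either.

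The 1.25 to 1.75 range for the odds ratio, with type I error of about 6% to 16%, is an assumption-driven upper bound on the extent of leakage through the monthly meetings, at 20% discordance and 25 patients per year. It is not a bound over discordance, since rarer discordant pairs would give larger distortion. It is not an estimate of what happened. The point deserves action because the risk falls on the primary outcome and closing it costs almost nothing.

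**What to change.** In the Quality Control / Interim Analysis section, split each meeting. Anyone who performs sensory testing (the evaluating residents, and the second observer if that person is not an operator) attends only an open part on logistics and progress, with no side- or instrument-specific information. Harms, benefit, case discussion by side or instrument, and any interim results go to a closed part without them. Apply the same rule to the later three-monthly meetings, and state whether the meeting resident is an evaluator.

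The cost is a sentence or two of protocol text and a divided agenda, with no extra staff. The small downside is that evaluators must report field problems in the open part or in writing. The existing rule that the principal investigator reviews initial adverse event reports immediately is unaffected.

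If conduct has ended, report instead who attended these meetings and whether allocation was discussed while assessors were present, next to the blinding-guess data.
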